**Table 8: Summary of Phase 2 Response Data in Melanoma (CA184022)**

	10 mg/kg (n = 72)	3 mg/kg (n = 72)	0.3 mg/kg (n = 73)
BORR (mWHO) – % (95% CI)	11.1 (4.9 - 20.7)	4.2 (0.9 - 11.7)	0 (0.0 - 4.9)
DCR (mWHO) – % (95% CI)	29.2 (19.0 - 41.1)	26.4 (16.7 - 38.1)	13.7 (6.8 - 23.8)
Survival rate at 1 year - % %, 95% CI	48.64 (36.84, 60.36)	39.32 (27.97, 50.87)	39.58 (28.20, 51.19)
Survival rate at 2 year - % %, 95% CI	29.81 (19.13, 41.14)	24.20 (14.42, 34.75)	18.43 (9.62, 28.22)
Overall median survival 95%CI (months)	11.43 (6.90, 16.10)	8.74 (6.87, 12.12)	8.57 (7.69, 12.71)

Finally, the dose and schedule in study CA184156 is the one that was evaluated in the signal finding study CA184041, with an acceptable safety profile and improvement of irPFS and OS.

Treatment with ipilimumab has demonstrated clinically important and durable tumor responses in several malignancies including melanoma, prostate cancer, and renal cell carcinoma.

### **1.3.7.e Advanced Melanoma**

Ipilimumab prolonged survival in subjects with pre-treated advanced melanoma are based on results from MDX010-20 (Phase 3) supported by data from Phase 2 studies; the primary efficacy and safety studies are summarized in Table 9. The primary endpoint in MDX010-20 was OS, which was also a key secondary endpoint in Phase 2 studies.

**Table 9: Studies Supporting the Efficacy and Safety of Ipilimumab in Subjects with Advanced Melanoma**

Study No. (Phase)	Populations	Primary Efficacy Endpoint	Doses Studies	# Randomized or Enrolled/Treated		
				3 mg/kg	10 mg/kg	Total

**Table 9: Studies Supporting the Efficacy and Safety of Ipilimumab in Subjects with Advanced Melanoma**

				# Randomized or Enrolled/Treated		
MDX010-20 (Phase 3)	HLA-A2*0201-positive, previously treated, unresectable Stage III or IV melanoma	OS	3 mg/kg q3 wk x 4 ± gp100 (induction) followed by re-induction	540/512	--/--	676/643 a
CA184022 (Phase 2)	Previously treated, unresectable Stage III or IV melanoma	BORR	0.3, 3, or 10 mg/kg q3 wk x 4 (induction) followed by maintenance dosing q12 wk	72/71	72/71	217/214
CA184004 (Phase 2) Biomarker Study	Unresectable Stage III or IV melanoma	BORR	3 or 10 mg/kg q3 wk x 4 (induction) followed by maintenance dosing q12 wk	40/40	42/42	82/82
CA184008 (Phase 2)	Previously treated unresectable State III or IV melanoma	BORR	10 mg/kg q3 wk x 4 (induction) followed by maintenance dosing q12 wk	--/--	155/155	155/155
CA184007	Unresectable Stage III or IV melanoma	BORR	10 mg/kg q3 wk x 4 ± budesonide (induction) followed by maintenance dosing q12 wk	--/--	115/115	115/115
Additional Studies						
MDX010-08 (Phase 2)	Chemotherapy-naive advanced melanoma	ORR	3 mg/kg q4 wk x 4 ± DTIC (induction)	78/74	--/--	78/74
CA184042 (Phase 2)	Stage IV melanoma with brain metastases	DCR	10 mg/kg q3 wk x 4 (induction) followed by maintenance dosing q12 wk	--/--	28/28 b	28/28 b

**Table 9: Studies Supporting the Efficacy and Safety of Ipilimumab in Subjects with Advanced Melanoma**

				# Randomized or Enrolled/Treated		
MDX010-28 (Phase 2) Survival Follow-up Study	Subjects enrolled in earlier Medarex studies, including MDX010-08 and MDX010-15 c	OS	N/A	--/N/A	--/NA	--/N/A

BORR = best overall response rate; DCR = disease control rate; DTIC = dacarbazine; N/A = not applicable; ORR = overall response rate; OS = overall survival; PK = pharmacokinetics.

a Total includes 136 randomized/131 treated subjects in the gp100 treatment group.

b Information is presented only for subjects enrolled in MDX010-20, Arm A.

c MDX010-15 was primarily a PK study that evaluated ipilimumab at single and multiple doses.

Source: Reference 16-23

### **1.3.7.f Rationale for combining Nivolumab with ipilimumab**

The combination of nivolumab and ipilimumab was chosen as an experimental arm because of preclinical and preliminary clinical evidence suggesting synergy between nivolumab and ipilimumab. While PD-1 and CTLA-4 are both co-inhibitory molecules, evidence suggests that they use distinct mechanisms to limit T cell activation. Preliminary indirect data from peripheral T cell assessments suggest that a given T-cell checkpoint inhibitor may modulate host immune cell phenotype rendering them more susceptible to alternate checkpoint inhibitors and thereby enhancing anti-tumor activity. Specifically, nivolumab increased peripheral CTLA-4+ and regulatory T cells in subjects without clinical response in CA209006. In a preclinical melanoma model, anti-CTLA-4 therapy increased PD-1+, PD-L1+ and CTLA-4+ tumor infiltrating T cells. In addition, in the Phase 2 ipilimumab monotherapy study CA184004, increases in tumor infiltrating lymphocytes (TILs) and interferon- $\alpha$ -inducible genes were observed following treatment with ipilimumab, and PD-L1 positive tumor cells co-localize with both TILs and IFN- $\alpha$  expression in metastatic melanoma.

The preliminary clinical evidence has demonstrated a higher frequency of patients with substantial tumor burden reduction for the combination of nivolumab and ipilimumab.

Improved overall survival associated with substantial tumor burden reduction has been noted with immunotherapies. For instance, improved overall survival has been noted in metastatic melanoma subjects obtaining a complete response to IL-2. If this observation is also applicable to treatment with nivolumab combined with ipilimumab then there could also be the potential for large improvements in overall survival compared to ipilimumab.

### **Dose and Schedule Rationale**

In CA209004, the 3 mg/kg nivolumab and 3 mg/kg ipilimumab cohort exceeded the maximum tolerated dose per protocol. In CA209004, while both Cohort 2 (1 mg/kg nivolumab + 3 mg/kg ipilimumab) and Cohort 2a (3 mg/kg nivolumab + 1 mg/kg ipilimumab) had similar clinical activity, a dose of 3 mg/kg of ipilimumab every 3 weeks for a total of four doses and 1 mg/kg nivolumab every 3 weeks for four doses followed by nivolumab 3mg/kg every 2 weeks until progression was chosen. Exposure-response analysis of nivolumab monotherapy across dose ranges of 1 mg/kg to 10 mg/kg reveals similar clinical activity while exposure-response analysis of 0.3 mg/kg, 3 mg/kg, and 10 mg/kg of ipilimumab monotherapy have demonstrated increasing activity with increase in dose in the phase 2 study CA184022. Therefore, theoretically the selection of 3 mg/kg of ipilimumab (Cohort 2) may be more clinically impactful than selection of 3 mg/kg of nivolumab (Cohort 2a).

The combination arm has a similar dose and schedule as that in CA209004 for the first 12 weeks, increasing the likelihood of replicating the clinical activity seen in the CA209004 study. Based on the clinical activity in CA209004, the majority of responses to the combination of nivolumab and ipilimumab occur in the first 12 weeks. Given the uncertainty of whether the ipilimumab administered past week 12 contributes to the clinical benefit and the fact that the approved schedule for ipilimumab is every 3 weeks for a total of four doses in the FDA and EMA approved label dosing section, ipilimumab will only be administered every 3 weeks for a total of 4 doses. Nivolumab monotherapy treatment every two weeks until progression was studied in CA209003 and is implemented program-wide across the nivolumab monotherapy Phase 3 registrational trials.

Nivolumab monotherapy has been extensively studied in a number of tumor types including non-small cell lung cancer (NSCLC), melanoma, renal cell carcinoma (RCC), and colorectal cancer (CRC) with body weight normalized dosing (mg/kg). Nivolumab pharmacokinetics (PK) and exposures of subjects in these studies have been characterized by population pharmacokinetic (PPK) analysis of data collected in these studies, together

with PK data from several Phase 1, 2, and 3 clinical studies of nivolumab monotherapy in solid tumors. PPK analyses have shown that the PK of nivolumab are linear, with dose proportional exposures over a dose range of 0.1 mg/kg to 10 mg/kg, and are similar across tumor types. Nivolumab clearance and volume of distribution were found to increase with increasing body weight, but the increase was less than proportional, indicating that a mg/kg dose represents an over-adjustment for the effect of body weight on nivolumab PK. Given the relationship between nivolumab PK and body weight, a flat dose is expected to lead to lower exposures in heavier patients, relative to the exposures in lighter patients.

Using the PPK model, nivolumab steady-state trough, peak and time-averaged concentration ( $C_{minss}$ ,  $C_{maxss}$ , and  $C_{avgss}$ , respectively) were predicted for a flat nivolumab dose of 240 mg Q2W and compared to those following administration of 3 mg/kg Q2W in NSCLC, melanoma, and RCC subjects. A dose of 240 mg nivolumab is identical to a dose of 3 mg/kg for subjects weighing ~ 80 kg, which is the approximate median body weight of subjects in the Phase 2 and 3 BMS clinical studies of nivolumab monotherapy. From the simulations, the geometric mean values of  $C_{minss}$ ,  $C_{maxss}$ , and  $C_{avgss}$  with flat dosing are slightly (< 15%) higher than that produced by a 3 mg/kg dose, and the coefficient of variation (cv%) in these measures of exposure are only slightly (< 10%) greater than that of 3 mg/kg dosing. Given the similarity of nivolumab PK across tumor types and the similar exposures predicted following administration of a 240 mg flat dose compared to 3 mg/kg, it is expected that the safety and efficacy profile of nivolumab following a flat dose will be similar to that of 3 mg/kg nivolumab dose.

Across the various tumor types in the BMS clinical program, nivolumab has been shown to be safe and well tolerated up to a dose level of 10 mg/kg, and the relationship between nivolumab exposure produced by 3 mg/kg and efficacy has been found to be relatively flat. Taken together, the PK, safety, and efficacy data indicate that the safety and efficacy profile of flat nivolumab dose every 2 weeks will be similar to that of a 3 mg/kg nivolumab every 2 weeks. In this study after completion of the combination portion of the study, all subjects will receive flat dose 480 mg nivolumab every 4 weeks (Q4W), which provides a more convenient dosing regimen for subjects. Based on PK modeling and simulations, administration of nivolumab 480 mg Q4W will be started after steady state is achieved with the combination regimen. While 480 mg Q4W is predicted to provide greater (approximately 20%) maximum steady state concentrations and lower (approximately 10%) steady state trough concentrations, these exposures are predicted to be within the exposure ranges observed at doses up to 10 mg/kg Q2W used in the Phase 1 nivolumab clinical program, and are not considered to put subjects at increased risk. Similar to

the nivolumab Q2W dosing monotherapy regimen, the exposures predicted following administration of nivolumab 480 mg Q4W, are on the flat part of the exposure-response curves for previously investigated tumors, melanoma and NSCLC, and are not predicted to affect efficacy. Based on these data, nivolumab 480 mg Q4W is expected to have similar efficacy and safety profiles to nivolumab 3 mg/kg Q2W.

Hence, doubling the dose of nivolumab from 240 mg to 480 mg would extend the dosing interval from 2 weeks to 4 weeks. Thus a flat dose of 480 mg every 4 weeks is recommended for investigation in the maintenance phase of this study.

### ***1.3.7. g Rationale for Permitting Continued Treatment in Select Cases of Progressive Disease***

Accumulating clinical evidence indicates some subjects treated with immune system stimulating agents may develop progression of disease (by conventional response criteria) before demonstrating clinical objective responses and/or stable disease. This phenomenon was observed in approximately 10% of subjects in the Phase 1 study of nivolumab and also with ipilimumab monotherapy. Two hypotheses have been put forth to explain this phenomenon. First, enhanced inflammation within tumors could lead to an increase in tumor size which would appear as enlarged index lesions and as newly visible small non-index lesions. Over time, both the malignant and inflammatory portions of the mass may then decrease leading to overt signs of clinical improvement. Alternatively, in some individuals, the kinetics of tumor growth may initially outpace anti-tumor immune activity. With sufficient time, the anti-tumor activity will dominate and become clinically apparent. Therefore, subjects will be allowed to continue study therapy after initial investigator-assessed RECIST 1.1 defined progression if they are assessed to be deriving clinical benefit and tolerating study drug.

## **1.4 Overall Risk/Benefit Assessment**

There continues to be a significant unmet need for patients with previously untreated, **unresectable or metastatic uveal melanoma**.

Nivolumab monotherapy has demonstrated clinical activity across several tumor types, including advanced prior treated melanoma, with objective response rates of 20 - 41% in 106 melanoma subjects treated at various dose levels in CA209003. Nivolumab has also demonstrated a manageable safety profile. The most common AEs included fatigue, rash, pruritis, diarrhea, and nausea.

The combination of nivolumab and ipilimumab has the potential for increased benefit compared to both ipilimumab monotherapy and nivolumab monotherapy. Preliminary analysis of the evaluable CA209004 subjects revealed that approximately 33% of the subjects had >80% tumor reductions in target lesions by week 12. This compares favorably to < 2% for 3 mg/kg ipilimumab monotherapy based on the CA184020 (N=540) and <3% for nivolumab monotherapy based on the CA209003. However, the combination of nivolumab and ipilimumab also has the potential for increased frequencies of adverse events. The most common (reported at > 10% incidence) treatment related AEs are fatigue, rash, pruritus, diarrhea, lipase increased, pyrexia, ALT increase, AST increased, amylase increased and vitiligo. Although the preliminary data suggests an increase in adverse event frequency of nivolumab combined with ipilimumab compared to ipilimumab monotherapy or nivolumab monotherapy, there were no unexpected adverse events noted in the combination of nivolumab and ipilimumab. In addition, many of the Grade 3-4 adverse events associated with the nivolumab combined with ipilimumab were laboratory in nature, without clinical sequelae and adverse events have been manageable and reversible following intervention dose delays or with systemic steroid treatment.

Evaluating the combination of nivolumab and ipilimumab will provide clinical data allowing clinicians to select the appropriate treatment for each patient based on the individual risk-benefit ratio. The robust clinical activity demonstrated by nivolumab monotherapy and the promising clinical activity of nivolumab combined with ipilimumab in subjects with advanced melanoma in combination with the manageable safety profile and the lack of approved survival-prolonging agents for a large segment of the previously untreated population supports the further development of nivolumab and nivolumab combined with ipilimumab in subjects with previously untreated, unresectable or metastatic melanoma.

## **1.5 Uveal Melanoma**

Uveal melanoma is the most common primary intraocular malignant tumor in adults and the second most common type of primary malignant melanoma in the body. It represents five to six percent of all melanoma diagnoses. The incidence of uveal melanoma in the world is approximately 4,800 persons per year with nearly 2,000 cases diagnosed in North America annually. Metastasis is via vascular spread, and approximately 40-50% of patients with uveal melanoma will ultimately develop distant disease. The liver is involved in up to 95% of individuals who develop metastatic disease. The clinical course of patients with uveal melanoma is determined by progression of the disease in the liver. Once metastatic disease is identified, the median survival of patients with liver metastases is six

to seven months, despite therapy, with a dismal one-year survival of approximately 10-15%.

Immunotherapy using checkpoint blockade inhibitors have made significant headway in cutaneous melanoma but their relevance in melanomas of rare subtypes, including uveal melanoma, remains unstudied in a prospective fashion. Anecdotal reports from expanded access programs and case reports of uveal melanoma patients treated with ipilimumab at both 3 mg/kg and 10 mg/kg demonstrate modest clinical activity at best with responses no more than 6%. CA184-187 was the first prospective ipilimumab trial in the world dedicated solely to uveal melanoma patients. After enrollment of 20 patients however, no documented responses were noted at both 3 mg/kg and 10 mg/kg.

Because of rationale behind combination checkpoint blockade inhibition and the notable clinical activity in cutaneous melanoma with a 1-year overall survival approaching that of targeted therapies (69% 1-year OS presented by Sznol et al. ASCO 2014), it is possible that monotherapy checkpoint blockade may not be enough to overcome tumor progression in uveal melanoma and that combination immunotherapy is in fact the necessary approach. Indeed, reports of small series of uveal melanoma patients on monotherapy anti-PD-1 clinical trials to date have failed to demonstrate any responses (nivolumab, MK-3475). Combination checkpoint blockade with nivolumab and ipilimumab at doses established in cutaneous melanoma warrant investigation in a prospective fashion for metastatic uveal melanoma patients.

The overall risk-benefit ratio for patients entering this protocol is therefore at least comparable to and possibly better than alternative options, specifically for uveal melanoma, where no standard therapies exist. Therefore, this protocol is at least comparable to the consensus recommendations for this population to enroll on some form of a clinical trial.

## **1.6 Study Rationale**

Metastatic uveal melanoma is uniformly fatal and median overall survival with current therapies remains poor (6 months) with 10-15% of patients surviving at one year. Ipilimumab has been safely used in uveal melanoma patients in the expanded access program both in the United States and in Europe. Anti PD-1 early clinical trials have enrolled few uveal melanoma patients with no notable responses, although administration was safe and tolerable. Combination nivolumab plus ipilimumab in cutaneous melanoma is marked by early tumor responses with significant regression in tumor burden. However,

uveal melanoma patients were not enrolled on this combination study. As noted in cutaneous melanoma, the combination of two checkpoint inhibitors may result in early and deep tumor responses for the population of patients with advanced uveal melanoma.

Metastatic uveal melanoma patients with at least one measurable lesion will be treated with nivolumab plus ipilimumab until disease progression or until unmanageable toxicity occurs.

## **2 STUDY OBJECTIVES**

### **2.1 Primary Objective**

The primary objective of this study is overall response rate

### **2.2 Secondary Objectives**

Secondary objectives include Safety and tolerability of combination, progression-free survival, median overall survival, and one-year overall survival.

### **2.3 Exploratory Objectives**

Exploratory Objectives include tissue and blood correlates to define immune infiltration and signatures as a result of treatment with nivolumab plus ipilimumab.

## **3. STUDY DESIGN**

### **3.1 Screening and registration**

[figure not shown]
Interested patients with uveal melanoma will be screened for eligibility as defined in Section 4. If all criteria are met, the patient will sign consent and be registered into the central database, Clinical Oncology Research System (CORG).

### **3.2 Study Schema**

This is a Phase II study of nivolumab combined with ipilimumab for metastatic uveal melanoma.

See illustrated schema on the following page.

**STUDY SCHEMA:**

### **3.3 Treatment**

Nivolumab is to be administered as a 60-minute IV infusion, using a volumetric pump with a 0.2/0.22 micron in-line filter at the protocol-specified dose. The drug can be diluted with 0.9% normal saline for delivery but the total drug concentration of the solution cannot be below 0.35 mg/ml. It is not to be administered as an IV push or bolus injection. At the end of the infusion, flush the line with a sufficient quantity of normal saline.

Ipilimumab is to be administered as a 90-minute IV infusion, using a volumetric pump with a 0.2 to 1.2 micron in-line filter at the protocol-specified dose. The drug can be diluted with 0.9% normal saline or 5% Dextrose Injection to concentrations between 1 mg/mL and 4 mg/mL. It is not to be administered as an IV push or bolus injection. Care must be taken to assure sterility of the prepared solutions, since the drug product does not contain any antimicrobial preservatives or bacteriostatic agents. At the end of the infusion, flush the line with a sufficient quantity of normal saline or 5% dextrose solution.

When both study drugs are to be administered on the same day, separate infusion bags and filters must be used for each infusion. Nivolumab is to be administered first. The nivolumab infusion must be promptly followed by a saline flush to clear the line of nivolumab before starting the ipilimumab infusion.

Baseline weight will be used to calculate all induction doses unless weight varies by +/- 10% from baseline. In that case, actual weight will be used.

#### ***3.2.1.a Induction Phase***

During the induction phase, patients will be treated with nivolumab 1 mg/kg plus ipilimumab 3 mg/kg (+/- 7 days) for a total of four doses (week 1, 4, 7, 10). The induction phase continues through week 12.

During the induction phase, patients will also have a mandatory biopsy of tumor tissue for exploratory immune biomarker studies. This biopsy can occur any time after cycle 1 until the end of cycle 4 (weeks 4-12).

#### ***3.2.1.b Maintenance Phase***

For patients who have not experienced disease progression, or unmanageable toxicity by week 12, a maintenance phase will begin. Maintenance treatment consists of nivolumab

monotherapy 480 mg/ every 4 weeks for up to 104 weeks or until disease progression or unmanageable toxicity as deemed by the clinical investigator.

During the maintenance phase and at the end of the study, patients have the option to undergo an additional biopsy of tumor tissue for exploratory biomarker studies.

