## PROTOCOL SYNOPSIS

Protocol Title:	Nivolumab in combination with Ipilimumab for uveal melanoma
Site Numbers & Names:	The University of Texas MD Anderson Cancer Center
Research Hypothesis:	Among patients with metastatic uveal melanoma, treatment with nivolumab plus ipilimumab will demonstrate safety, tolerability, and efficacy in improving overall response
Study Schema: Drugs / Doses / Length of Treatment)	
Metastatic uveal melanoma patients with at least one measureable lesion will be treated with nivolumab plus ipilimumab until disease progression or until unmanageable toxicity occurs.
 
The doses used will be nivolumab 1 mg/kg and ipilimumab 3 mg/kg, both intravenous (IV).
 
During the induction phase, patients will be treated with nivolumab 1 mg/kg IV plus ipilimumab 3 mg/kg IV every 3 weeks (+/- 7 days) for a total of four doses (week 1, 4, 7, 10). Treatment then continues at week 13 in the maintenance phase with nivolumab 480 mg IV every 4 weeks until disease progression or unacceptable toxicity.

Study Objectives: Primary: Secondary: Exploratory:	
PRIMARY OBJECTIVE: Overall response rate
 
SECONDARY OBJECTIVES: Progression-free survival, median overall survival, one-year overall survival
 
EXPLORATORY OBJECTIVES: Exploratory objectives include tissue and blood correlates to define immune infiltration and signatures as a result of treatment with nivolumab plus ipilimumab.

Study Design:	Phase II study of nivolumab plus ipilimumab for metastatic uveal melanoma.

Accrual Goal: (Total number of patients)	Metastatic uveal melanoma: Up to 39 patients to achieve 27 evaluable patients
Accrual Rate: (Number of patients expected per month)	2-4 patients per month
FPFV: LPFV: Follow Up: (dd-mmm-yy)	01-Aug-2014 05-Jan-2018 Until death or alternate treatment

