## 6 STUDY PROCEDURES AND OBSERVATIONS

### 6.1 Time and Events Schedule

**Table 10: Time and Events Schedule for Protocol**

Procedure	Baseline a	Week 1, 4, 7, 10	Week 13 and every 4 weeks thereafter	Week 13 and every 12 weeks thereafter	End of Study
Eligibility					
Consent	X				
Inclusion/Exclusion	X				
Medical History	X				
Safety Assessments					
Interim History	X	X	X		X
Physical Examination	X	X	X		X
Vital signs, Height c , Weight, Performance Status	X c	X	X		X
Adverse Events	X	X	X b		X
Concomitant Medications	X	X	X		X
Common Laboratory Tests	X	X	X b		X

Liver Function Tests	X	X	X b		X
Thyroid Function Tests	X	X		X	X
Pregnancy Test e	X	X			
Tumor Measurementsc	X			X	
Correlative studies d		X	X		X
Nivolumab infusion		X	X b		
Ipilimumab infusion		X			

- a. Baseline visit and Week 1 visit may occur simultaneously.
- b. Patients will have adverse event assessments, common laboratory tests, liver function tests, and treatment every 4 weeks thereafter until removed from study.
- c. Tumor assessments will occur at baseline, Week 13 and every 12 weeks thereafter until removed from study. Assessments will have a window of +/- 7 days and will be in the form of CT chest, abdomen, pelvis with oral and intravenous contrast or acceptable alternative body imaging at the discretion of the investigator. Brain imaging only at the discretion of the investigator.
- d. Mandatory biopsy one-time during induction weeks 4-12, optional biopsy during maintenance and at the end of study
- e. Pregnancy test will be every 4 weeks during Maintenance phase (every other visit).

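### Section 3.2.1.b caps maintenance nivolumab at 104 weeks, the synopsis and Section 1.6 state no maximum, and the documents also disagree on when scanning stops

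*Combined protocol and SAP*

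**What the plan says.** **Treatment duration**

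- Synopsis, Study Schema: maintenance starts at week 13 with "nivolumab 480 mg IV every 4 weeks until disease progression or unacceptable toxicity". The same cell says more generally that patients "will be treated with nivolumab plus ipilimumab until disease progression or until unmanageable toxicity occurs". Neither sentence has a maximum.
- Section 1.6 repeats the general statement: "nivolumab plus ipilimumab until disease progression or until unmanageable toxicity occurs".
- Section 3.2.1.b alone has a limit: nivolumab 480 mg "every 4 weeks for up to 104 weeks or until disease progression" or unmanageable toxicity. The 104-week figure appears nowhere else.
- Table 10 schedules infusions at week 13 and four-weekly after that, with no last week. Its note b has "treatment every 4 weeks thereafter until removed from study".

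**End of tumour assessment**

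- Synopsis, Criteria for Evaluation: efficacy is assessed at week 12 and 12-weekly after that, ending at progression or at treatment discontinuation.
- Section 9.1: assessment goes on until progression is documented or treatment stops, whichever is the later.
- Table 10 note c: assessments continue until the patient is removed from study.
- Section 3.4: patients who discontinue are followed to death or study closure. For those off treatment for toxicity or by investigator judgement, efficacy assessment is left to standard of care. Nothing is said specifically about a patient who completes a fixed course while still free of progression.

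**The concern.** Both the synopsis and Section 3.2.1.b are current operative text, and the documents give no order of precedence. A patient without progression or limiting toxicity at 104 weeks stops under one and continues under the other. Neither course could be called a protocol deviation with confidence.

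The two conflicts interact. PFS is a secondary objective, to be analysed by Kaplan-Meier (Section 9.2). If treatment stops at a cap and the synopsis rule ends scanning at the same visit, the patient's PFS is censored because treatment ended, although there has been no progression. That would fall on the patients doing best, who make up the tail of the curve. If Section 9.1 is followed, scanning goes on and this does not happen. The same applies to anyone who stops for toxicity before progression, so the scanning rule needs settling even if no cap is kept.

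**Working it through.** **1. Which passages conflict.**

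| Place | End of maintenance | Maximum |
|---|---|---|
| Synopsis, Study Schema | progression or toxicity | none stated |
| Section 1.6 | progression or toxicity | none stated |
| Section 3.2.1.b | progression or toxicity, or the limit | 104 weeks |
| Table 10, note b | removal from study | none stated |

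The synopsis and Section 3.2.1.b cannot both be followed in a patient who reaches the limit. Table 10 fits either, since removal from study could include removal at a cap.

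**2. Start point.** Section 3.2.1.b does not say from which week the 104 weeks are counted. With four-weekly dosing from week 13:

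- counted from the start of maintenance: weeks 13, 17, ..., 113, which is 26 doses;
- counted from study week 1: weeks 13, 17, ..., 101, which is 23 doses.

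The difference is 3 doses, or 12 weeks.

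**3. How many patients could reach the limit.** The documents give no expected time on treatment, so survival to two years (104 weeks is about 24 months) serves as an upper bound: a patient must be alive to be on treatment. The assumption is a constant hazard, applied to the 27 evaluable patients.

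- From the 10-15% one-year survival in Sections 1.5 and 1.6, S(24) = S(12)². This gives 0.10² = 0.010 and 0.15² = 0.0225. Times 27: 0.27 and 0.61 patients.
- From the 6-7 month median in Section 1.5 (patients with liver metastases), S(24) = 0.5^(24/median). This gives 0.5^(24/6) = 0.0625 and 0.5^(24/7) = 0.0929. Times 27: 1.7 and 2.5 patients.

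The two inputs do not agree under a constant hazard. Medians of 6 and 7 months imply one-year survival of 0.5^(12/6) = 25% and 0.5^(12/7) = 30%, against the stated 10-15%. Both ranges are therefore shown.

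These are historical rates. At the 20% response rate of the alternative hypothesis, 0.20 × 27 = 5.4 responders are expected. The documents give no duration of response in uveal melanoma from which to say how many would still be on treatment at two years.

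**4. Primary decision rule.** With X ~ Binomial(27, p), P(X ≥ 4) is 0.0437 at p = 0.05 and 0.8177 at p = 0.20, a type II error of 0.1823. These match the stated 4.4% and 18.2% in Section 9. Maintenance duration does not enter the calculation.

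**The case against.** The strongest reply is that much of this is already covered.

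- Section 9.1 is the efficacy section, and its rule keeps a patient who stops without progression on scans. A reader might infer from the synopsis that a 104-week cap necessarily ends scanning in responders and censors their PFS. The documents do not support that: it follows only under the synopsis rule. What stands is the conflict between the two. Section 9.1 also times its visits from randomization, which this single-arm trial does not have, so a site may be unsure that it governs.
- A reader might call Table 10 a further contradiction. It is not one, because its wording can accommodate a cap. Nor does the absence of a 104-week limit from the discontinuation list in Section 5.2.3 show anything, since that list does not name progression either.
- The general sentences in the synopsis and Section 1.6 are loose: read literally they continue both drugs, although ipilimumab is limited to four doses. That is fair, and it leaves the synopsis sentence on maintenance itself as the clearest conflict.
- The 104 weeks most naturally run from the start of maintenance, since the phrase describes maintenance treatment. The 12-week difference is thus a reason to state the start point, not a main finding.
- The two-year maximum mentioned in Section 1.3.6 belongs to another nivolumab study and decides nothing here.
- The secondary objectives are PFS, median overall survival and one-year overall survival. A limit acting at about two years cannot change one-year survival and is unlikely to move either median at the stated prognosis. This stands, and it keeps the point small.

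**Conclusion.** The duration conflict is real: Section 3.2.1.b has a 104-week limit that the synopsis and Section 1.6 lack, and nothing in the documents resolves it. The scan-stopping rule conflicts separately between the synopsis and Section 9.1, and the two meet in any patient who stops without progression.

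The likely reach is small: about 0.3 to 0.6 of 27 patients alive at two years on the stated one-year survival, and about 1.7 to 2.5 on the stated median. Both assume a constant hazard and historical survival, and both are upper bounds for patients still on treatment under those rates. It would be tempting to report about two patients as stopped by the cap and lost to PFS. That figure would treat survival as time on treatment, set aside the lower one-year figures, and assume the synopsis scanning rule. If the regimen is effective, more patients could be affected.

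The response-rate decision rule is unaffected. This is a minor point, worth correcting because correction is easy.

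**What to change.** 1. Reconcile the synopsis, Section 1.6, Section 3.2.1.b and Table 10 note b to one maintenance duration. If a limit is kept, state the week from which it is counted and that the earliest of the limit, progression and toxicity applies. Which duration is right is a clinical decision for the sponsor and investigator.
2. Align the synopsis rule on efficacy evaluation with Section 9.1, so that a patient who stops treatment without progression, including at any cap, is scanned until progression and the end of treatment does not itself censor PFS. Make Table 10 note c and Section 3.4 say the same.

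The cost is amendment wording, plus continued scans for the few patients who stop treatment before progression. Sample size, error rates and the primary analysis do not change.
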